5.7 Criteria for Taking a Participant Off Protocol Therapy

Duration of therapy will depend on individual response, evidence of disease progression and tolerance. In the absence of treatment delays due to adverse event(s), treatment may continue until one of the following criteria applies:

1. Disease progression by RECIST 1.1 criteria:
 - A. Participants who have attained a confirmed complete response (CR) that have been treated for at least 24 weeks on protocol therapy and had at least three cycles (with pembrolizumab and sacituzumab govitecan (Arm A) or sacituzumab govitecan alone (Arm B)) beyond the date when the initial CR was declared may be eligible for additional sacituzumab govitecan and/or pembrolizumab therapy if they progress after stopping study treatment. This retreatment is termed the Second Course Phase Therapy. See additional details below.
2. Dose reduction beyond 50% of sacituzumab govitecan requires stopping sacituzumab govitecan. The patient may continue on treatment with pembrolizumab until progression or up to 35 doses of pembrolizumab are completed, whichever comes first.
3. Intercurrent illness that prevents further administration of treatment.
4. Unacceptable adverse event(s).
5. Participant demonstrates an inability or unwillingness to comply with the medication regimen and/or documentation requirements.
6. Participant decides to withdraw from the protocol therapy.

Note: Participants on either treatment arm (Arm A or Arm B) may elect to stop therapy (sacituzumab govitecan and pembrolizumab OR sacituzumab govitecan only on either arm) with confirmed CR after at least 24 weeks of treatment. These participants are still required to undergo regular disease restaging every 9-12 weeks. Note: for participants on Arm A, if only sacituzumab govitecan is discontinued, Day 8 assessments (AE assessment, labs, vitals, etc.) are not needed.

7. General or specific changes in the participant's condition render the participant unacceptable for further treatment in the judgment of the treating investigator.

Participants will be removed from the protocol therapy when any of these criteria apply. The reason for removal from protocol therapy, and the date the participant was removed, must be documented in the case report form (CRF) and in the CTMS system (OnCore). Alternative care options will be discussed with the participant.

In the event of unusual or life-threatening complications, treating investigators must immediately notify the Sponsor-Investigator, [name], [contact], or email: [contact] .

Second Course Phase Therapy:

Retreatment Phase (available to both Arms)

Participants who stop sacituzumab govitecan and/or pembrolizumab with CR after at least 24 weeks of treatment may be eligible for additional pembrolizumab and/or sacituzumab govitecan therapy if they progress after stopping study treatment. For participants randomized to the combination arm (Arm A): if both sacituzumab govitecan and pembrolizumab are discontinued and participant experiences progression, both sacituzumab govitecan and pembrolizumab can be restarted at physician's discretion; or if sacituzumab govitecan is discontinued and pembrolizumab is continued and participant experiences progression, sacituzumab govitecan can be added to the pembrolizumab at physician's discretion. For participants randomized to sacituzumab govitecan monotherapy (Arm B): if sacituzumab govitecan is discontinued and participant experiences progression, sacituzumab govitecan can be restarted at physician's discretion. This retreatment is termed the Second Course Phase of this study and is only available if the study remains open and the subject meets the following conditions:

- Stopped initial treatment with sacituzumab govitecan and/or pembrolizumab after attaining an investigator-assessed CR according to RECIST 1.1, confirmed in at least two consecutive restaging scans, was treated for at least 24 weeks with pembrolizumab and/or sacituzumab govitecan before discontinuing therapy, and received at least three cycles (with pembrolizumab and sacituzumab govitecan (Arm A) or sacituzumab govitecan alone (Arm B)) beyond the date when the initial CR was declared

AND

- Experienced an investigator-assessed or radiographic disease progression after stopping their initial treatment with sacituzumab govitecan and/or pembrolizumab (Arm A) or sacituzumab govitecan (Arm B)
- Did not receive any anti-cancer treatment other than:
 - Arm A: Sacituzumab govitecan (or pembrolizumab) since the last dose of pembrolizumab (or sacituzumab govitecan)
 - Arm B: No other anti-cancer treatment since the last dose of sacituzumab govitecan

- Participants who stop pembrolizumab after receiving 35 doses may be eligible for retreatment if they progress after stopping study treatment, provided they meet the requirements detailed in Sections 3.3 and 3.4. Participants may be retreated in the Second Course Phase (Retreatment) for up to an additional 17 cycles (approximately 1 year).

The retreatment section of the eligibility checklist should be completed and signed by the treating investigator. DF/HCC sites will re-send the checklist to ODQ for processing. Non-DF/HCC sites will email documentation to the Coordinating Center at [contact] for review. Provided the patient meets criteria per protocol for retreatment, the Coordinating Center will process the checklist and the participating site will be notified that the patient may proceed to retreatment.

Subjects who restart treatment will be retreated at the same dose and dose interval as when they last received pembrolizumab and/or sacituzumab govitecan. Visit requirements are as outlined for subjects on the initial treatment phase of the trial. These participants may resume the scan schedule they had previously during the treatment break, i.e., every 9 weeks.

5.8 Duration of Follow Up

Participants will be followed on-study until death. Participants removed from protocol therapy for unacceptable adverse event(s) will be followed until resolution or stabilization of the adverse event. An additional adverse event assessment will be performed 90 days (-15/+30 days) after the last dose of treatment for participants who receive pembrolizumab, including participants who stopped early for CR, are candidates for retreatment, and have not yet restarted pembrolizumab. This may be conducted by phone.

Participants who discontinued therapy for reasons other than progression will be followed for first disease progression or until the start of another anti-cancer therapy. Tumor assessments should continue to be performed every 9-12 weeks on these participants until first disease progression event, start of another anti-cancer therapy, or death, whichever occurs first. Research bloods are optional at the time of tumor assessments. At either the time of disease progression or start of another anti-cancer therapy, participants will then be followed for survival.

Participants will be followed or contacted every 6 months for survival.

5.9 Criteria for Taking a Participant Off Study

Participants will be removed from study when any of the following criteria apply:

- Lost to follow-up
- Withdrawal of consent for data submission
- Death

The reason for taking a participant off study, and the date the participant was removed, must be documented in the case report form (CRF). In addition, the study team will ensure Off

Treatment/Off Study information is updated in OnCore in accordance with DF/HCC policy REGIST-OP-1.

6 DOSING DELAYS/DOSE MODIFICATIONS

Dose delays and modifications will be made as indicated in the following table(s). The descriptions and grading scales found in the revised NCI Common Terminology Criteria for Adverse Events (CTCAE) version 5.0 will be utilized for dose delays and dose modifications. A copy of the CTCAE version 5.0 can be downloaded from the CTEP website: http://ctep.cancer.gov/protocolDevelopment/electronic_applications/ctc.htm.

6.1 Dosing Delays/Omission/Modifications

Dosing interruptions within a 7-day window are permitted in the case of medical / surgical events or logistical reasons not related to study therapy (e.g., elective surgery, unrelated medical events, patient vacation, and/or holidays). Participants with doses held for these reasons for more than 7 days require prior approval from the Sponsor-Investigator and should resume therapy within 6 weeks of the scheduled interruption. The reason for interruption should be documented in the participant's study record. If a dose is held on day 1 of a cycle, the cycle restarts when the participant meets criteria to start; the assessment schedule should be adjusted accordingly.

In the absence of an unacceptable therapy-related toxicity and/or clinical signs of disease progression, subjects may continue treatment at the discretion of the investigator. Subjects must be instructed to notify their physician immediately for any and all toxicities.

Guidelines for the management of AEs (i.e., dose interruptions and dose reductions) and recommendations for treating expected toxicities are presented in the next sections. Consultation with a medical or surgical specialist, especially prior to an invasive diagnostic or therapeutic procedure, is recommended. For management of AEs which can be clearly attributed to sacituzumab govitecan or pembrolizumab, independent dose modification for either agent is allowed. For AEs without clear attribution to either study treatment, management of toxicity should include dose modifications of both agents.

6.1.1 Management of Dosing Delays/Interruptions/Modifications attributable to Pembrolizumab or Sacituzumab Govitecan:

Pembrolizumab should be held (delayed) or omitted for toxicities that are considered possibly, probably or definitely related to pembrolizumab (per Section 6.2 guidance). Sacituzumab govitecan should be held (delayed), dose reduced, or omitted for toxicities that are considered possibly, probably or definitely related to sacituzumab govitecan (per Section 6.3 guidance). If on arm A (first course or retreatment), either drug may be discontinued, while the other drug continues.

- If a subject on Arm A does not meet criteria for treatment (Section 5.2) due to a toxicity that is considered attributable to only one of the drugs of the combination (e.g., platelets $60,000/\text{mm}^3$ attributed to sacituzumab govitecan), the drug causing the toxicity should be

held, and the other study drug may be administered (unless specified in the corresponding AE table of that study drug).

- For subjects on Arm A, if one study drug is delayed but the other study drug is given, then the study drug that was held should be re-initiated if appropriate at the next regularly scheduled administration time, i.e. if held on day 1 of the cycle, then sacituzumab govitecan could be restarted on day 8 of the cycle or day 1 of the next cycle (\pm 2 days for Day 1) and pembrolizumab could be restarted on day 1 of the next cycle (\pm 4 days).
- There must be a minimum of 14 days (\pm 2 days) between Day 8 and Day 1 of the next cycle of sacituzumab govitecan. There should be a minimum of 21 days \pm 4 days between administration of each dose of pembrolizumab.
- If treatment with sacituzumab govitecan is held or omitted due to an AE and the patient cannot be retreated with sacituzumab govitecan within 6 weeks from the last dose, sacituzumab govitecan should be permanently discontinued. Pembrolizumab can be continued per protocol (if the AE is considered unrelated to pembrolizumab).
- If treatment with pembrolizumab is held or omitted due to an AE and the patient cannot be retreated with pembrolizumab within 9 weeks from the last dose, pembrolizumab should be permanently discontinued. Sacituzumab govitecan can be continued per protocol (if the AE is considered unrelated to sacituzumab govitecan).
- For subjects on Arm A, if sacituzumab govitecan is discontinued and pembrolizumab is continued, Day 8 assessments (AE assessment, labs, vitals, etc.) are not needed.

6.1.2 Management of Diarrhea

Diarrhea requires special attention, as it can be caused by either study drug. See Section 6.2 and 6.3 for additional diarrhea management guidelines for pembrolizumab and sacituzumab govitecan, respectively. At enrollment, patients should receive instructions on the management of diarrhea. In the event of diarrhea, supportive measures should be initiated as early as possible. These include the following:

- At the first sign of loose stools, the patient should initiate anti-diarrheal therapy (for example, loperamide) and notify the investigator/site for further instructions and appropriate follow-up.
- Patients should also be encouraged to drink fluids (for example, 8 to 10 glasses of hydrating liquids per day).
- Site personnel should assess response within 24 hours.
- If diarrhea does not resolve with anti-diarrheal therapy within 24 hours to either baseline or Grade 1, both study drugs should be suspended until diarrhea is resolved to baseline or Grade 1.
- When sacituzumab govitecan recommences, dosing should be adjusted as outlined in Table 6 in Section 6.3.

In cases of significant diarrhea, grade 2 through 4, which has not responded to the above interventions, and which has not been determined to be related to another cause (i.e. infection such as *C. difficile*), an endoscopic procedure to document colitis prior to initiating steroids is strongly recommended if the addition of steroids to treat potential colitis is being considered.

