6.3 Management of Toxicities Attributable to Sacituzumab Govitecan

NCI-CTCAE v5.0 is used to grade the severity of all AEs. The guidelines for management of toxicities associated with sacituzumab govitecan are based on the assessment of severity according to these criteria. Toxicities should be managed in accordance with standard medical practice and treatment guidelines. All clinically appropriate imaging or laboratory testing should be utilized to fully assess a toxicity to determine the appropriate treatment. Appropriate follow-up studies should be utilized to follow all toxicities to resolution. Patients with known UGT1A1 *28 polymorphism may have a higher risk of developing treatment related toxicities. Additional monitoring may be required in those patients.

Dose Delays – Sacituzumab Govitecan

Sacituzumab govitecan is to be administered in 21-day cycles on Day 1 and Day 8; the next cycle should start 14 days (\pm 2 days) after the Day 8 dose (i.e., the Day 8 infusion will be counted as the first day of that 14-day period). Visit windows of \pm 2 days from the scheduled infusion are permitted. The scheduled Day 1 and Day 8 infusions may be delayed for treatment-related toxicities. For Day 8 dosing, if the toxicity has not resolved to \leq Grade 2 within 1 week, Day 8 dosing of that cycle should be omitted and dosing should resume with the Day 1 of the following cycle. There should be a minimum of 7 days (\pm 2 days) between the Day 1 and the Day 8 infusions. There should be a minimum of 14 days (\pm 2 days) between the Day 8 infusion and the Day 1 infusion of the next cycle.

For patients randomized to the combination arm, if drugs are administered on different days in the same 21-day cycle, every effort should be made to administer both drugs on the same day in subsequent cycles (all assessments being adjusted accordingly), provided that criteria are met per protocol and that 14 days (\pm 2 days) have elapsed since the administration of the previous dose of sacituzumab govitecan and 21 \pm 4 days since the administration of the previous dose of pembrolizumab. If Day 8 sacituzumab govitecan dosing is delayed, causing adjustment to Day 1 of the following cycle, it is recommended to administer pembrolizumab on the same day as Day 1 of the next cycle of sacituzumab govitecan.

Dose Reductions and Discontinuation

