**Sacituzumab govitecan may be dose reduced for recurring Grade 2 diarrhea that is not controlled with antidiarrheal agents.

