6.3.2 Sacituzumab Govitecan Gastrointestinal Toxicities

Nausea, vomiting, and diarrhea are frequent sacituzumab govitecan-associated toxicities. Appropriate treatment, including, as needed, fluid and electrolyte replacement, is required to minimize the risk of serious consequences such as dehydration. Instructions for Sacituzumab Govitecan dose reduction for treatment-related gastrointestinal toxicities are provided above in Table 6.

Nausea and Vomiting

Instructions for the use of pre-medications for prophylactic treatment of nausea and vomiting and anticipatory nausea are provided in Section 5.3.1. Do not hold the dose of sacituzumab govitecan for Grade 3 nausea unless Grade 3 nausea persists despite maximal optimal medical management. Subjects should be treated for delayed nausea and vomiting on Days 2 and 3 with 5-HT₃ receptor antagonist (ondansetron or palonosetron) monotherapy and other agents if needed. Steroids may be added if symptoms do not resolve with these other agents. Consider olanzapine for persistent or anticipatory nausea; an olanzapine dose of 2.5 mg or 5 mg at bedtime is recommended. NK1 receptor antagonists (fosaprepitant and aprepitant) may be administered.

Diarrhea

Dietary modification should be recommended for the management of diarrhea, including a bland diet, small frequent meals, adequate fluid intake of clear liquids to maintain hydration, and discontinuation of lactose-containing foods and drinks containing alcohol. Loperamide should be administered at the onset of treatment-related diarrhea, at an initial dose of 4 mg, followed by 2 mg with every episode of diarrhea, to a maximum dose of 16 mg/day. If diarrhea is not resolved after 24 hours, add diphenoxylate/atropine or opium tincture as clinically indicated.

Add octreotide 100-150 mcg subcutaneously 3 times per day (tid) if diarrhea persists. For Grade 4 diarrhea, consider subject hospitalization and treatment with IV fluids and octreotide. Antibiotics can be administered as clinically indicated.

Subjects who exhibit an excessive cholinergic response to treatment with sacituzumab govitecan (e.g., abdominal cramping, diarrhea, salivation, etc.) can receive appropriate premedication (e.g., atropine) for subsequent treatments.

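### Sections 6.1.2 and 6.3 set different recovery levels for a Day 8 sacituzumab dose after diarrhea, and neither is said to take precedence

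*Combined protocol and SAP*

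**What the plan says.** Section 6.1.2 (Management of Diarrhea) is specific to this toxicity. Its trigger is "If diarrhea does not resolve with anti-diarrheal therapy within 24 hours to either baseline or Grade 1", and its action is that "both study drugs should be suspended until diarrhea is resolved to baseline or Grade 1". It has no separate provision for Day 8. It then sends the dose on restart to Table 6, and it points to other sections: "See Section 6.2 and 6.3 for additional diarrhea management guidelines for pembrolizumab and sacituzumab govitecan, respectively".

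Section 6.3 (Management of Toxicities Attributable to Sacituzumab Govitecan) covers treatment-related toxicity in general. Its delay rule is permissive: "The scheduled Day 1 and Day 8 infusions may be delayed for treatment-related toxicities". The next sentence begins "For Day 8 dosing, if the toxicity has not resolved to" and, after a less-than-or-equal sign, gives the threshold and the action: "Grade 2 within 1 week, Day 8 dosing of that cycle should be omitted and dosing should resume with the Day 1 of the following" (quoted up to its last word). Diarrhea is not excepted.

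Three other places bear on the point:

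- Section 6.1.1 says that sacituzumab is to be held, reduced or omitted for related toxicity according to Section 6.3.
- Section 5.2.2, the laboratory criteria for Day 8 and for later Day 1 doses, lists neutrophils, platelets, bilirubin, transaminases and creatinine. It has no diarrhea item.
- The Table 6 footnote says that sacituzumab "may be dose reduced for recurring Grade 2 diarrhea that is not controlled with antidiarrheal agents", and Section 6.3.2 says "If diarrhea is not resolved after 24 hours, add diphenoxylate/atropine or opium tincture as clinically indicated".

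**The concern.** Two recovery levels are stated for the same drug. One is baseline or Grade 1, for diarrhea. The other is Grade 2 or lower within a week, for any toxicity before a Day 8 dose. A site that goes to Section 6.3, as Section 6.1.1 directs, finds no instruction there to suspend for Grade 2 diarrhea. A site that goes to Section 6.1.2 finds one.

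What is at stake is patient protection and consistent sacituzumab exposure. Sacituzumab is given in both arms of an open-label trial. Section 7.1.2 reports diarrhea in 62% of patients in the earlier sacituzumab safety population, 9% at Grade 3 or higher, so this is a common toxicity. Holds also have consequences: under Section 6.1.1, a patient who cannot be retreated within 6 weeks of the last dose because of an adverse event stops sacituzumab permanently.

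**Working it through.** The plan gives no figure to reproduce and no arithmetic applies. The check is to run each possible state of diarrhea at a Day 8 visit through both rules.

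| Diarrhea when Day 8 sacituzumab is due | Section 6.1.2 | Section 6.3, Day 8 sentence | Same action? |
|---|---|---|---|
| Baseline or Grade 1 | Not suspended | Not omitted | Yes |
| Grade 3-4, still above Grade 2 after a week | Suspended | Omitted | Yes |
| Grade 2, persisting after 24 hours of anti-diarrheal therapy | Suspended | Omission not triggered | No |
| Grade 3-4, improved only to Grade 2 | Suspended | Omission not triggered | No |

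The rules agree at both ends and part only where the diarrhea is at Grade 2. In those two rows Section 6.1.2 keeps the drug suspended, while the condition for omission in Section 6.3 is not met. If the diarrhea is still Grade 2 when the week allowed for a delayed Day 8 dose runs out, the first rule says not yet and the second does not call for omission. Neither says what becomes of that dose.

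Next, does anything settle the order?

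1. Section 6.1.2 describes Section 6.3 as further guidance on diarrhea. This does not say that either yields to the other.
2. Section 6.1.1 names Section 6.3 as the reference for sacituzumab holds and makes no mention of Section 6.1.2.
3. Section 5.2.2 has no diarrhea criterion that could break the tie.
4. Section 6.3 does not exempt diarrhea from its Day 8 sentence.

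Finally, do the Table 6 footnote and Section 6.3.2 add to the conflict? They do not. Section 6.1.2 sends the dose on restart to Table 6, so an optional reduction for recurring Grade 2 diarrhea can follow a hold. Section 6.3.2 gives supportive drug treatment, and a second anti-diarrheal can be added while sacituzumab is suspended. Neither mentions the hold, but silence is not contradiction.

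**The case against.** The strongest reply is that the specific rule governs the general one. Section 6.1.2 is devoted to diarrhea, singles it out for special attention, and treats Section 6.3 as supplementary. On that reading the Day 8 sentence is a backstop for toxicities in general and leaves the diarrhea hold intact. Table 6 lends some support: for Grade 3 or higher toxicity that delays a dose by 2 or 3 weeks, it measures recovery to Grade 1 or lower.

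Much of this stands. It is a natural reading, and a site that dosed through persisting Grade 2 diarrhea would be departing from the text of Section 6.1.2. It remains a reading, however. The protocol does not state it, and Section 6.1.1 points sacituzumab holds the other way, to Section 6.3. The Table 6 rows concern longer delays after Grade 3 or higher events. They do not cover diarrhea that began at Grade 2, and they do not say that the Day 8 sentence gives way.

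A reader might also infer that the same patient is both ordered held and ordered dosed. The documents do not support that. Section 6.3 never directs a dose at Grade 2. It allows one only by implication from an omission rule, so a site that holds under Section 6.1.2 complies with both sections.

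**Conclusion.** The point holds as an unresolved difference between a diarrhea-specific rule and a general Day 8 rule, with no stated precedence. It is confined to Day 8 sacituzumab doses due when diarrhea is at Grade 2, either persisting on therapy or improved from Grade 3-4. It is more than missing detail, because two stated recovery levels lead to different actions for the same patient on a common toxicity. It assumes that Section 6.1.2 applies in Arm B to the one drug given there.

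The number of patients affected cannot be derived. A reader might try Section 7.1.2: 62% - 9% = 53% with a worst grade of 1-2, and 0.53 x 110 = about 58 patients. That is not a count of conflict cases. The Grade 2 share is not given, and worst grade over a whole treatment course does not show whether Grade 2 diarrhea persisted at a Day 8 visit. The subtraction also drops Grade 3-4 cases that improved only to Grade 2.

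Nor do the documents support a claim about the trial's efficacy inference. No effect on PFS, power or type I error follows from this wording. The one planned between-arm toxicity test in Section 13.6 is of any Grade 3 or higher toxicity, so no formal comparison of Grade 2 diarrhea is at risk.

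**What to change.** The sponsor must reconcile Section 6.1.2 with the Day 8 sentence in Section 6.3. One statement should say which rule governs a Day 8 sacituzumab dose after diarrhea, and what happens to that dose if the diarrhea is still at Grade 2 when the one-week delay expires. The clinical team chooses the grade; this review takes no position on it. The Table 6 footnote and Section 6.3.2 need only a cross-reference to the hold.

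The cost is protocol wording, with no new data, visits or patients. Section 13.2.1 reports accrual as complete, so the change would serve patients still on treatment or entering the Second Course Phase.
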